8.3.2 Investigator reporting: Notifying the FDA

This protocol is being conducted under an FDA investigational new drug application. The sponsor-investigator will report to the FDA all unexpected, serious suspected adverse reactions according to the required IND Safety Reporting timelines, formats and requirements. Unexpected fatal or life threatening suspected adverse reactions where there is evidence to suggest a causal relationship between the study drug/placebo and the adverse event, will be reported as a serious suspected adverse reaction. This will be reported to the FDA on FDA Form 3500A, no later than 7 calendar days after the sponsor-investigator's initial receipt of the information about the event.

Other unexpected serious suspected adverse reactions where there is evidence to suggest a causal relationship between the study drug/placebo and the adverse event, will be reported as a serious suspected adverse reaction. This will be reported to the FDA on FDA Form 3500A, no later than 15 calendar days after the sponsor-investigator's initial receipt of the information about the event.

Any clinically important increase in the rate of serious suspected adverse reactions over those listed in the protocol or product insert will be reported as a serious suspected adverse reaction. This will be reported to the FDA on FDA Form 3500A no later than 15 calendar days after the sponsor-investigator's initial receipt of the information about the event. The sponsor-investigator must also notify the FDA (and sponsors must notify all participating investigators) in an IND safety report of potential serious risks, from clinical trials or any other source, as soon as possible, but in no case later than 15 calendar days after the sponsor determines that the information qualifies for reporting under § 312.32(c)(1)(i)-(iv). Findings from other studies in human or animals that suggest a significant risk in humans exposed to the drug will be reported. This will be reported to the FDA on FDA Form 3500A, no later than 15 calendar days after the sponsor-investigators initial receipt of the information about the event.

8.4 Unmasking/Unblinding Procedures

This is an open-label pilot investigation. Unmasking/unblinding procedures are not applicable.

8.5 Stopping Rules

This investigation is of low risk to study subjects. Stopping or interruption of the study may be necessary if a significant number of participants develop an unexpectedly severe dermatitis that does not resolve with decreased frequency of application.

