4.4 Early Withdrawal of Subjects

4.4.1 When and How to Withdraw Subjects

Patients are free to withdraw at any time and for whatever reason. No data will be collected for withdrawn subjects and withdrawn subjects will not be replaced. There will be no follow-up for withdrawn subjects. Pre-specified reasons for discontinuing include, but are not limited to, the following:

- Patient request: Patient decided that he/she did not want to continue (for any reason).
- •Adverse Event: Patient experienced a related or unrelated event that would interfere with the study objectives/evaluation
- •Lost to Follow-up: Patient did not come in for a visit and could not be reached by phone
- Treatment Failure: If in the Principal Investigator's judgment, the patient's condition required another form of treatment
- •Noncompliance: Patient is not complying with the protocol requirements (i.e. visit schedule, dosing, regimen, etc.); a patient is to be withdrawn if he/she misses two consecutive visits
- •Other: Any other reason

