4.4.2 Data Collection and Follow-up for Withdrawn Subjects

If a Participant withdraws from the study, no additional attempts will be made to contact the Participant.

5 Study Drug

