5.2 Study Procedures

Preparation and Administration of Study Drug

Each participant will receive both verbal and written instructions as to proper dosing and application and storage. The Mayo Clinic Research Pharmacy in Rochester, MN will prepare, store and distribute the study formulation. Participants will receive 2-one-half pound ointment jars of the study formulation. The jars will be returned the final visit.. The returned used jars will be weighed by the Principal Investigator or a study team member to determine the amount used/compliance. Should additional cream be required during the 2 weeks of the study, the patient can contact the principal investigator or the clinical study coordinator. Upon notification from the patient, an extra ½ pound jar will be sent to the patient by overnight express mail.

Instructions will be provided as follows: Twice daily, apply a thin film of the study formulation to symptomatic areas of the skin including about one centimeter of normal appearing skin surrounding each area of involvement. Rub lightly and uniformly into the skin. An investigator will demonstrate correct application by using a bland emollient moisturizer.

Subject Compliance Monitoring

Adherence to the treatment regimen is of great importance. Poor compliance may result from lack of patient understanding, discomfort caused by the product and unrealistic expectations. Assessment of participant compliance will be determined by weighing ointment jars at the time of the final visit. Participants are not expected to use a specific amount of the study formulation . Rather, use will be individualized depending on the amount of symptomatically involved skin. Those who are non-compliant with the study protocol despite additional counseling and the opportunity to correct will be withdrawn.

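### The only stated stopping trigger (8.5) requires dermatitis to persist at a reduced application frequency, but the visible plan has no reduction step and no scheduled contact to check its result; 4.4 also conflicts with the adverse event follow-up in 8.1–8.2

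*Combined protocol and SAP*

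**What the plan says.** **Stopping.** Section 8.5 calls the study low risk and says that stopping or interruption may be needed "if a significant number of participants develop an unexpectedly severe dermatitis that does not resolve with decreased frequency of application". No other study-level trigger is given, and section 7.2 plans no interim analysis.

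**Dosing.** The instruction in 5.2 is "Twice daily, apply a thin film of the study formulation to symptomatic areas of the skin". Section 5.2 lets the amount vary with the area of involved skin, but the frequency is fixed and no reduction or interruption step is described. Under compliance monitoring, it says: "Poor compliance may result from lack of patient understanding, discomfort caused by the product and unrealistic expectations". It then adds: "Those who are non-compliant with the study protocol despite additional counseling and the opportunity to correct will be withdrawn".

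**Contacts.** Sections 6.1, 6.5 and 6.6 schedule Visit 1 (week 0, dispensing) and Visit 2 (week 2, plus or minus 1 day), which is the final visit, when the cream is reconciled. Section 3.4 measures local skin tolerability, the primary safety endpoint, at those two visits.

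**Withdrawal.** Section 4.4.1 lists an adverse event among the reasons for discontinuing and states: "No data will be collected for withdrawn subjects and withdrawn subjects will not be replaced". It also rules out follow-up. Section 4.4.2 adds that after a withdrawal "no additional attempts will be made to contact the Participant".

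**Adverse event follow-up.** Sections 8.1 and 8.2 require unresolved events to be followed until they resolve, stabilize or are otherwise accounted for, and require questioning about events at every contact. Neither section says whether it or 4.4 governs a withdrawn patient.

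**The concern.** A stopping rule should be answerable from what the study plans to observe. This one depends on the outcome of a dose-frequency reduction that the visible plan neither directs nor schedules anyone to check. Section 3.4 expects little systemic absorption, so local skin reaction is the main foreseeable harm, and 8.5 is the only study-level rule that addresses it. If severe reactions appear at Visit 2 in several patients who applied the cream twice daily as told, the stated rule gives no direction on whether to dispense to the next participant.

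The withdrawal text adds a second problem. A patient with a bad reaction is a likely candidate for withdrawal, and 4.4 can end observation at the point where the later course of the dermatitis, on which 8.5 depends, would be seen.

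**Working it through.** The plan gives no stopping count, no dermatitis rate and no sample size calculation, so there is no figure to reproduce. The check is mainly a comparison of sections. I take treatment as two weeks, as in 6.5, 6.6 and the duration rows of the Study Summary, although its regimen row says four weeks.

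**Step 1: what the trigger needs.**
- One contact on treatment, to find severe dermatitis and reduce the frequency.
- A later contact, to see that it has not resolved.

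That makes 2 contacts after dispensing.

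**Step 2: what is scheduled.** There are 2 visits in total and 1 is the dispensing visit, so 2 − 1 = 1 contact remains. It coincides with the end of treatment, so 0 scheduled contacts fall between dispensing and the end of treatment. Scheduled procedures alone cannot evaluate the trigger.

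**Step 3: how the trigger could still be met.**
- The patient makes unscheduled contact and the investigator advises a lower frequency. The only between-visit contact described (5.2) is a request for more cream, though 8.2 would then require questioning about adverse events.
- The patient cuts back unprompted and says so at Visit 2. Jar weight would not show it, since "Participants are not expected to use a specific amount of the study formulation".
- A reaction found at Visit 2 is followed under 8.1–8.2, and persistence after application has ended is read as meeting 8.5. Ending application is not literally a decreased frequency, so this needs a broad reading.

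**Step 4: withdrawal.** Sections 4.4.1–4.4.2 say no data, no follow-up and no contact. Sections 8.1–8.2 say follow the event. If 4.4 is applied, dermatitis given as the reason for withdrawal is known but its later course is not. If 8.1–8.2 are applied, both are known. The text supports either practice.

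**Illustration only.** Every input here is assumed: severe dermatitis rate p, share q of cases that can count under 8.5, a pause at the second counted case, each outcome known before the next patient starts, and no use of discretion. The chance of pausing before patient 10 is

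P(Bin(9, pq) ≥ 2) = 1 − (1 − pq)^9 − 9pq(1 − pq)^8

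- pq = 0.40: 1 − 0.0101 − 0.0605 = 0.929
- pq = 0.20: 1 − 0.1342 − 0.3020 = 0.564
- pq = 0.10: 1 − 0.3874 − 0.3874 = 0.225

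| Assumed p | q = 1 | q = 0.5 | q = 0 |
|---|---|---|---|
| 0.40 | 0.929 | 0.564 | 0 |
| 0.20 | 0.564 | 0.225 | 0 |

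With a pause at the third case and p = 0.40, the figures are 0.768, 0.262 and 0. The table shows only the direction: the fewer cases the condition lets through, the less the rule can do. It does not estimate risk in this study.

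**The case against.** The strongest reply is that 8.5 is permissive. It says when stopping may be called for, not that this is the only case. Investigators oversee safety (8.6), review all adverse event reports (8.3.1), can class an event as serious on their own opinion (8.1), and report qualifying events to the IRB and FDA (8.3.1, 8.3.2). All of this stands, and it limits the point to the written rule. It does not remove the point: 8.6 regularly assesses serious events only, and severe dermatitis need not be classed as serious.

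A reader might go further in three ways that the documents do not support.
- **That the trigger can never be met, so cases found at Visit 2 count for nothing at any rate.** This takes the narrowest reading. The routes in step 3 exist, and follow-up under 8.1–8.2 could show persistence.
- **That a patient who cuts back because of a reaction will be withdrawn as non-compliant.** Section 4.4.1 does list departures from dosing or regimen, and 5.2 names discomfort as a cause of poor compliance. But withdrawal comes only after counseling and a chance to correct, compliance is assessed at the final visit, and 8.5 itself contemplates a lower frequency. The text is unclear, but it sets no firm trap.
- **That outcomes after withdrawal will be lost.** They can be, but 8.1–8.2 point the other way.

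The written instructions promised in 5.2 and the Patient Handout are not visible and could contain a reduction step or advice to call. If so, the first half of the gap narrows, though a check of the result before Visit 2 would still be needed.

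It is also fair to say that this is a 10-patient, two-week pilot of ingredients already in clinical use. That bears on how likely the rule is to be needed, not on whether it works as written.

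**Conclusion.** The point holds in limited form. As the visible protocol stands, the one stated trigger needs 2 contacts after dispensing and 1 is scheduled, at the end of treatment. Severe dermatitis first found there in a patient on twice-daily use does not literally meet 8.5, and meeting the trigger depends on unplanned events or a broad reading. The separate conflict between 4.4.1–4.4.2 and 8.1–8.2 is plain on the page.

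The gap is in the study-level rule. It would be wrong to infer that individual patients are unprotected or that investigators cannot stop. The undefined size of a significant number is missing detail and is not the basis of this point.

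The conclusion rests on reading the sections together and on the unseen patient instructions not supplying a reduction step. It does not rest on the illustrative probabilities. Because the remedy is nearly free and concerns the primary safety endpoint, the change should be made, with medium confidence in how much it would matter in practice.

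**What to change.** **(a) Section 8.5.** Base the trigger on severe dermatitis of treated skin and drop the reduced-frequency condition. If the sponsor prefers to keep the condition, add to 5.2 a reduction directed by the investigator, state that it is not noncompliance, and schedule one phone call before Visit 2 to check the result.

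**(b) Sections 4.4.1–4.4.2.** State that adverse events in withdrawn patients are recorded, followed under 8.1–8.2 unless the patient declines contact, and considered under 8.5.

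**Cost.** Wording changes, plus one call per patient if the condition is kept. The downside is slightly less discretion and a possible unneeded pause, which is reversible.

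**Optional.** The sponsor could set a pause count in advance and check the running number before each dispensing. For each outcome to be known first, starts must be at least 15 days apart (14 days plus the 1-day window): 9 × 15 = 135 days from first to tenth start, within the one-year study. The trade-off is false pauses: at an assumed 10% rate, a count of 2 would pause about 23% of such studies before patient 10 and a count of 3 about 5%; at 5%, about 7% and 0.8%. Changes (a) and (b) do not depend on this.

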8.6 Medical Monitoring

It is the responsibility of the Principal Investigator and Investigators to oversee the safety of the study. This safety monitoring will include careful assessment and appropriate reporting of adverse events as noted above. Medical monitoring will include a regular assessment of the number and type of serious adverse events.

9 Data Handling and Record Keeping

9.1 Confidentiality

Information about study subjects will be kept confidential and managed according to the requirements of the Health Insurance Portability and Accountability Act of 1996 (HIPPA). Those regulations require a signed subject authorization informing the subject of the following:

- What protected health information (PHI) will be collected from subjects in this study
- Who will have access to that information and why
- Who will use or disclose that information
- The rights of a research subject to revoke their authorization for use of their PHI

In the event that a subject revokes authorization to collect or use PHI, the Principal Investigator and Investigators, by regulation, retain the ability to use all information collected prior to the revocation of subject authorization. For subjects that have revoked authorization to collect or use PHI, attempts will be made to obtain permission to collect at least vital status (long term survival status that the subject is alive) at the end of their scheduled study period.

9.2 Source Documents

Source data is all information, original records of clinical findings, observations, or other activities in a clinical trial necessary for the reconstruction and evaluation of the trial. Source data are contained in source documents. Examples of these original documents, and data records include: hospital records, clinical and office charts, laboratory notes, memoranda, subjects' diaries or evaluation checklists, pharmacy dispensing records, recorded data from automated instruments, copies or transcriptions certified after verification as being accurate and complete, micorfiches, photographic negatives, microfilm or magnetic media, x-rays, subject files, and records kept at the pharmacy, at the laboratories, and at medico-technical departments involved in the clinical trial.

All source documents including clinical findings, observations or other activities will be stored in a REDCap database that will be designated by the Statistician. Access to the REDCap database will be limited to the Principal Investigator, Investigators, and Statistician.

9.3 Case Report Forms

All data requested on the Case Report Form (CRF) will be recorded for each participant. A standardized CRF will be generated by REDCap. All missing data will be explained. If a space on the CRF is left blank because the question was not asked, "N/D" will be recorded. If the item is not applicable to the individual case, "N/A" will be recorded. If any entry error has been made, a single straight line through the incorrect entry will be drawn and the correct data will be written above it. All such changes will be initialed and dated. Errors will not be erased or whited-

out. For clarification of illegible or uncertain entries, a clarification will be printed above the item, then initialed and dated. If the reason for the correction is not clear or needs additional explanation, details to justify the correction will be neatly included.

Data Management, Processing, Security and Confidentiality

Study data to be collected and managed using REDCap electronic data capture tools hosted at the Mayo Clinic. REDCap (Research Electronic Data Capture) is a secure, web-based application designed to support data capture for research studies, providing 1) an intuitive interface for validated data entry; 2) audit trails for tracking data manipulation and export procedures; 3) automated export procedures for seamless data downloads to common statistical packages; and 4) procedures for importing data from external sources.

Data Quality Assurance

Once the study is completed the Principal Investigator will randomly select 5 participants and compare the data documented for each on the CRF with what is entered into the REDCap database. If there is any discrepancy, the Principal Investigator and/or Investigators will cross-reference all 10 patients to ensure accuracy.

Data Clarification Process

For any data query the Principal Investigator and Investigators will meet to clarify the data queried and make corrections based on consensus.

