7.1 Sample Size determination

Due to the pilot nature of the study, no formal statistical power/sample size calculations are necessary. The sample size of 10 patients will be sufficient for this pilot study to obtain a preliminary estimate of treatment efficacy and to generate data that will be useful in the design of a larger study.

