7.2.1 Definition of response

Complete response:

Clinically significant SCORMA improvement in all 3 parameters of treated, involved skin: % skin involvement; activity or symptoms &/or

Improvement in all 3 SkinDex-16 domains (Emotions, symptoms, functioning) &/or Resolution of 75% of cutaneous lesions

Near Complete response:

Clinically significant SCORMA improvement in two of 3 parameters of treated, involved skin: % skin involvement; activity or symptoms and/or

Improvement in 2 SkinDex-16 domains (Emotions, symptoms, functioning) &/or Resolution of >50% of cutaneous lesions

Partial Response:

Clinically significant SCORMA improvement in one 3 parameters of treated, involved skin: % skin involvement; activity or symptoms and/or

Improvement in 1 SkinDex-16 domain (Emotions, symptoms, or functioning) &/or Resolution of >25% of cutaneous lesions

No response:

No significant SCORMA improvement in any of 3 parameters of treated, involved skin: % skin involvement; activity or symptoms and/or

Improvement in no SkinDex-16 domain (Emotions, symptoms, functioning) &/or Resolution of no cutaneous lesions.

*Additionally, for primary safety endpoints which will be scored as none, mild, moderate, or severe, the proportion of patients in each category at each follow-up time point will be estimated for each of the different safety endpoints. P-values of 0.05 or lower will be considered as statistically significant.

Handling of missing data

This is a prospective study and therefore we do not anticipate any missing data. In the event of any unexpected missing data, no attempt to impute this missing data will be made; missing data will simply be treated as missing in the statistical analysis.

Multiplicity

Since this is an exploratory pilot study, no adjustment for multiple testing is needed. P-value of 0.05 or lower will be considered as statistically significant.

Primary Hypothesis:

The study seeks to demonstrate the effectiveness and tolerability of a novel topical composition consisting of 3 components (diphenhydramine, aspirin and cromolyn sodium) in a neutral skin moisturizing cream (Vanicream) for the treatment of cutaneous lesions of mastocytosis. This will be determined by the proportion of participants who achieve complete or near-complete response utilizing the SCORMA Index, and SkinDex-16 QOL.

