7.3 Subject Populations(s) for Analysis

Each participant who received the study drug will be included in the primary analysis regardless of study withdrawal for any reason. In the event of any study withdrawals, in secondary analysis we will examine the sensitivity of our results to the exclusion of patients who withdrew.

8 Safety and Adverse Events

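### The CRF-to-database check on 5 of 10 participants, extended to all 10 only if it finds a discrepancy, misses a lone mis-entered record half the time; checking the key fields for all 10 is a cheap improvement

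*Combined protocol and SAP*

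**What the plan says.** The Data Quality Assurance paragraph of section 9.3 sets a two-stage check after study completion. First, "the Principal Investigator will randomly select 5 participants", whose CRFs are then checked against their REDCap entries. Second, "If there is any discrepancy, the Principal Investigator and/or Investigators will cross-reference all 10 patients to ensure accuracy". No reason is given for choosing 5, and no tolerable error rate is stated. The paragraph does not say whether the check comes before the analysis.

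The data set is small. Section 7.1 states that "The sample size of 10 patients will be sufficient for this pilot study". Under section 7.2.1 the primary question is settled by a proportion: "This will be determined by the proportion of participants who achieve complete or near-complete response utilizing the SCORMA Index, and SkinDex-16 QOL". Section 7.3 fixes the denominator: "Each participant who received the study drug will be included in the primary analysis regardless of study withdrawal for any reason". Section 4.4.1 adds that "No data will be collected for withdrawn subjects and withdrawn subjects will not be replaced", so fewer than 10 may have week 2 data.

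Other controls are described. Section 9.3 mentions validated data entry and audit trails in REDCap and a process for resolving queries. Section 10.1 has the institution's research regulatory support office review subject records, among other documents. It does not say how many records, which fields, or whether database values are compared with the CRF.

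**The concern.** Sampling for source-to-database comparison makes sense when a full comparison is expensive. Here the whole trial is 10 participants with two visits each, and the plan already accepts a full comparison whenever the sample shows any discrepancy. The escalation rule works well when errors are spread over several participants. It cannot help when the only mis-entered record lies among the five not drawn, because the sample is then clean and the check stops.

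The primary result is a count out of 10, so one participant's category carries visible weight. The response definitions in section 7.2.1 can turn on small differences. They set no minimum size for improvement in a SkinDex-16 domain, and they join the criteria with and/or. Read literally, one mis-keyed item could turn an unchanged domain into an improved one. A patient who goes from one improved domain to two moves from partial to near-complete, which is the boundary that counts for the primary proportion.

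**Working it through.** The plan states no detection probability, so there is no figure of its own to reproduce.

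**Inputs.** N = 10 participants (section 7.1); n = 5 sampled at random, with any discrepancy leading to all 10 (section 9.3). Assumptions not in the documents: the comparison always finds a discrepancy in a sampled record, and no other control finds one.

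**Step 1: chance that the check misses every bad record.** With k mis-entered participants, all are missed only if none is drawn. If even one is drawn, all 10 are compared. So P(all missed) = C(10−k, 5) / C(10, 5), with C(10, 5) = 252.

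| Bad records k | C(10−k, 5) | P(all missed) |
|---|---|---|
| 1 | 126 | 50.0% |
| 2 | 56 | 22.2% |
| 3 | 21 | 8.3% |
| 4 | 6 | 2.4% |
| 5 | 1 | 0.4% |
| 6 or more | 0 | 0% |

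**Step 2: overall chance, with an assumed error rate.** Step 1 is conditional on errors being present. Let p be the chance that a participant's record contains an entry error, independently between participants. Errors exist and are all missed when the five sampled records are clean and at least one of the other five is not: (1−p)^5 × [1 − (1−p)^5].

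| Assumed p | Any error among 10 | Errors exist and all missed |
|---|---|---|
| 1% | 9.6% | 4.7% |
| 2% | 18.3% | 8.7% |
| 5% | 40.1% | 17.5% |
| 10% | 65.1% | 24.2% |
| 20% | 89.3% | 22.0% |

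For p = 5%: 0.95^5 = 0.774, and 0.774 × 0.226 = 0.175. The expression has the form x(1−x), so it cannot exceed 25% at any p.

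**Step 3: weight of one participant.** 1/10 = 10 percentage points. If fewer have data, and the five are drawn from those who do, the weight rises and the single-record miss rate falls: 11.1 points and 44.4% with 9, 12.5 points and 37.5% with 8, 14.3 points and 28.6% with 7.

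**Step 4: effect of checking more.** With one bad record and n checked, the miss rate is (10−n)/10: 40% for n = 6, 30% for 7, 20% for 8, 10% for 9, and 0 for 10.

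**The case against.** The strongest reply is that this is a stated, reasonable two-stage procedure for an uncontrolled pilot with no formal power calculation. It examines half the participants, tolerates no discrepancy, and breaks no standard set elsewhere in the documents. That stands: the point is a design choice, and the plan does not contradict itself.

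The reply also has force against a stronger reading. From the 50% and the 10 points, a reader might infer an even chance that the primary result is wrong by 10 points. The documents do not support that:

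- The 50% applies only if exactly one record is wrong, and no error rate is given.
- Ten points is a ceiling. Many errors would leave the category unchanged. The and/or wording may let a patient qualify by another route, and the response forms carry their own assessment column, so a mistyped score need not alter the recorded category.
- Validated entry and the record review in section 10.1 may catch some errors. Validation cannot reject a plausible wrong value, such as a 2 keyed as a 3, and the extent of the record review is not stated. These controls therefore do not clearly close the gap.

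It is also unclear how much hand transcription takes place. Section 9.3 says the CRF is generated by REDCap, yet describes pen-and-initial corrections and a CRF-to-REDCap comparison. If entry is largely direct, there is less for this check to find. Finally, an error already on the CRF survives any comparison of CRF with database, however many participants are included.

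**Conclusion.** The concern holds as a minor one. A lone mis-entered record passes the planned check with probability 50%, and escalation is then not triggered. The rule does better as errors spread over more participants: 22%, 8% and 2% for two, three and four bad records. Under assumed per-participant error rates of 1% to 20%, the chance that errors exist and are all missed runs from about 5% to 24%.

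These figures assume 10 participants with data, independent errors, a comparison that never overlooks a discrepancy in a sampled record, and no other effective safeguard. A less careful comparison would make them worse; effective monitoring would make them better. The effect on the primary proportion is at most 10 points per undetected error, and only where the error crosses the near-complete/partial boundary. The documents do not allow the probability of such a crossing to be estimated.

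**What to change.** Amend the Data Quality Assurance paragraph of section 9.3 so that, before analysis, CRF and REDCap are compared for all 10 participants on the SCORMA components (global and local), the SkinDex-16 items, the response category and the safety table. Keep the random sample of 5, with escalation to all 10, for the remaining fields.

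For CRF-to-database discrepancies in those key fields, this takes the single-record miss rate from 50% to 0, given a careful comparison. The cost is five more two-visit records for the same person to compare. Counting from the attached forms, that is about 16 SkinDex-16 items, 10 global and 10 local SCORMA entries, and 4 safety items by two raters, or 44 values per visit. Over 5 participants and 2 visits this makes about 440 values, plus the response categories.

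Two limits remain. Errors made on the CRF itself would not be caught. The fields left to the sample, including the mediator levels that form the secondary endpoints in section 3.3, would keep the miss rates in the first table.
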